### **Statistical Analysis Plan**

We have estimated a necessary sample size of 50 participants per group (100 total) with an anticipated effect size of 0.54 based on estimated means of 17mm for the experimental arm (SD 20mm) and 29mm for the control arm (SD 24mm), accounting for expected loss to follow up of 10%. Patients were randomized using 10 block groups of size 10 each.

We will provide a table of demographic and clinical characteristics by assigned group. For continuous variables, we will provide means and standard deviations per group, applying a t-test for comparison of independent means. For categorical variables, we will provide counts and percentages, applying chi-square test for comparison of proportions.

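### Does leaving out alpha, sidedness and power make the sample size of 50 per group unsound?

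*Combined protocol and SAP*

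**What the plan says.** The whole justification is in the sample size paragraph of the Statistical Analysis Plan. The size and effect size are "We have estimated a necessary sample size of 50 participants per group (100 total) with an anticipated effect size of 0.54". The inputs are "estimated means of 17mm for the experimental arm (SD 20mm) and 29mm for the control arm (SD 24mm"), and the number is described as "accounting for expected loss to follow up of 10" per cent. Allocation is described in the past tense: "Patients were randomized using 10 block groups of size 10 each".

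The only test named for continuous variables comes in the next paragraph, "applying a t-test for comparison of independent means". It follows the sentence "We will provide a table of demographic and clinical characteristics by assigned group", so applying it to the millimetre outcome is an inference. That outcome is not named. The pain visual analogue scale is the only listed measure that plausibly fits. It appears under Visit 2 (Day 1) and is not listed under Visit 3.

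No section states alpha, one- or two-sided testing, or a target power.

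**The concern.** A sample size is necessary only relative to an error rate and a power, and the plan gives neither. A reader who supplies the usual two-sided 5% and 80% finds 50 per group too small, even with no loss to follow-up. On that reading a true 12 mm benefit would be missed about 28% of the time, against the 20% usually accepted.

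The missing sidedness also seems to leave the verdict open. If alpha is 5%, some observed differences would be significant one-sided and not significant two-sided, and the plan does not say which applies.

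**Working it through.** **Inputs from the sample size paragraph.** Means 17 and 29 mm (difference 12 mm), SDs 20 and 24 mm, 10% loss, 50 per group. The loss is already included, so 50 × 0.9 = 45 are evaluable per group. Alpha, sidedness and power are not given, so everything after the effect size rests on assumed values.

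**Effect size.** SD = √((20² + 24²)/2) = √488 = 22.09; d = 12/22.09 = 0.543. The stated 0.54 reproduces.

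**Sizes under different settings.** The normal approximation is n = (z_α + z_β)² × (20² + 24²)/12² = (z_α + z_β)² × 6.778. For two-sided 5% and 80% power: (1.960 + 0.842)² × 6.778 = 53.2, so 54. The t-test (noncentral t) gives slightly more. Enrolled = evaluable/0.9, rounded up.

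| Assumed setting | Normal approx. | t-test, d = 0.543 | Enrolled | Enrolled if d = 0.54 |
|---|---|---|---|---|
| Two-sided 5%, 80% | 54 | 54.2, so 55 | 62 | 62 |
| Two-sided 5%, 70% | 42 | 42.8, so 43 | 48 | 49 |
| One-sided 5%, 80% | 42 | 42.6, so 43 | 48 | 49 |
| Two-sided 10%, 80% | 42 | 42.6, so 43 | 48 | 49 |
| One-sided 10%, 90% | 45 | 44.95, so 45 | 50 | 52 |

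An enrolment of 48 or 49 per group is 96 to 98 in total, which rounds to 100 when patients are randomised in ten blocks of ten. Four of the five settings therefore fit 50 per group at d = 0.543. Only two-sided 5% with 80% power clearly does not.

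**Power at the planned size, alpha assumed to be 5%.**

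| Per group | Two-sided | One-sided |
|---|---|---|
| 45 | 72.2% | 81.9% |
| 50 | 76.7% | 85.4% |

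At 45 per group, d = 0.54 gives 71.7% and 81.5%, and allowing for unequal variances leaves the first row unchanged. The difference detectable with 80% power, two-sided, is 13.2 mm at 45 and 12.5 mm at 50, against 12 mm planned.

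**Significance thresholds at 45 per group.** SE = √(400/45 + 576/45) = 4.657 mm. Two-sided 5%: 1.987 × 4.657 ≈ 9.3 mm. One-sided 5%: 1.662 × 4.657 ≈ 7.7 mm. The verdict differs only for an observed benefit between these two values.

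**Does the size make a null result unusually hard to read?** At 45 per group, a null result with an observed benefit above 12 − 9.3 = 2.7 mm still has 12 mm inside its 95% interval. At 55 per group, which gives 80% power two-sided, SE = √(976/55) = 4.213, the half-width is 1.982 × 4.213 = 8.35 mm, and the same happens above 12 − 8.35 = 3.65 mm. A conventionally powered trial has nearly the same limitation.

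**The case for a change.** The strongest case for a change is that several incompatible designs fit the same number, so the plan ought to say which one was used. Unless it does, sidedness could be chosen after the data are seen, and a result between 7.7 and 9.3 mm could be called either way. One or two sentences would close the gap without another patient.

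The omission stands, and so do the conditional figures. The rest is weaker. The 7.7 to 9.3 mm window depends on a 5% alpha that the plan does not state. A t-test named without qualification is ordinarily run two-sided at 5%. A one-sided claim would need prior support that this document does not provide, so a later switch would be open to challenge. The proposed sentences would have to come from a planning record that is not among the documents. Adding them would not change how the data are collected or how a sensible analyst tests them. Since the plan speaks of randomisation as already done, a power figure written now would describe the trial without improving it.

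The 72% also charges the full 10% loss to the outcome. If that outcome is the Day 1 pain score, losses may be smaller and two-sided power closer to 77%. This softens the shortfall but does not remove it, because 77% is still below 80%.

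**Conclusion.** No change follows. The plan omits alpha, sidedness and power, so its 50 per group cannot be verified, but no stated figure is shown to be wrong. The effect size reproduces, and 50 is consistent with several settings on the stated inputs.

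If the test is two-sided at 5%, power for 12 mm is about 72% with 45 evaluable per group and 77% with 50. That assumes the planned SDs hold and that the t-test applies to the millimetre outcome. It is modest power, but it affects the chance of detecting the effect, not the validity of the test or the estimate. The ordinary two-sided 5% analysis, reported with its confidence interval, gives a sound result under the plan as written. This is missing detail that analysts fill sensibly.

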## Study Protocol

The process of insufflation will be used on all laparoscopic gynecological surgical patients and for the research protocol the amount of carbon dioxide measuring 12 mmHg used for the experimental group B is less than the standard amount of 15 mmHg used for the control group A. Insufflation pressures of either 12 mmHg (group B) or 15 mmHg (group A) will be used for this research, regardless of the subject's BMI, however it is noted that for patients with extreme upper BMIs, visualization can be more challenging. BMI will be one of the data points recorded for patients, however the randomization of the subjects to 12 mmHg (group B) or 15 mmHg (group A) will not be dependent on their BMI. Our maximum BMI for inclusion of subjects will be a BMI of 55.0.

Procedures other than Treatments:

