### Visit 1 (Day 0)

- Give informed consent at routine doctor visit (this will take an additional 30-45 min) – for research purposes only
- Information such as your age, weight, height, and medical history such as [previous heart attacks, etc.] will be copied from your medical record. Specifically, the following items will be collected: age, race, ethnicity, insurance status (public vs. private), body mass index (BMI), additional medical health conditions, surgical history-prior abdominal surgery, history of chronic pain, history of prior chronic opioid use, pre-operative medications – opioid/analgesic, history of alcohol and tobacco use, history of depression/anxiety; (this will take an additional 30-45 min) – for standard of care and for research purposes;

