### Visit 2 (Day 1)

- Post-anesthesia randomization to group A or group B, (this will take an additional 5-10 min) – for research purposes only;
- Intra-operative insufflation using 15 mmHg (standard-group A) or 12 mmHg (experimental-group B), adjustment of intra-operative insufflation pressure; (this will take an additional 5 min-10 min) – insufflation for group A is done as standard of care; insufflation for group B is done for research purposes only;
- Post-operative assessment to include the procedure details: indication for procedure, length, estimated blood loss, surgical complications, estimated blood loss, pathology, visual analog scale (VAS), pain medication – prescribed and taken, length of hospital stay, (this will take an additional 30-45 min) – for standard care and for research purposes;

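### Procedure type is handled in neither the allocation nor the analysis and is not named among the recorded items: a loss of precision, not bias, that one pre-specified covariate can recover

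*Combined protocol and SAP*

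**What the plan says.** **Population.** The Study Protocol section says "The process of insufflation will be used on all laparoscopic gynecological surgical patients". The only eligibility limit in the text available is a maximum BMI of 55.0.

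**Allocation.** The Statistical Analysis Plan says "Patients were randomized using 10 block groups of size 10 each". No stratification factor is named. The Study Protocol section adds that "the randomization of the subjects to 12 mmHg (group B) or 15 mmHg (group A) will not be dependent on their BMI". Visit 2 places allocation after anesthesia: "Post-anesthesia randomization to group A or group B".

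**Analysis.** For continuous variables the plan is "applying a t-test for comparison of independent means". No covariate is mentioned. The sentence follows the description of the characteristics table. It is the only method given for continuous variables, so I take it to be the VAS comparison as well.

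**Recorded items.** Visit 2 lists "Post-operative assessment to include the procedure details: indication for procedure, length, estimated blood loss, surgical complications", followed by pathology, VAS, pain medication and hospital stay. Visit 1 lists "surgical history-prior abdominal surgery", which is history and not the index operation. Neither list names the operation.

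**The concern.** Laparoscopic gynecological surgery covers short and long operations, and the type of operation plausibly affects post-operative pain. Blocking equalizes the numbers per arm but not the mix of operations. If procedure enters neither the allocation nor the model, its contribution to pain counts as noise, and the comparison is less precise than the same 100 patients could provide.

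If the operation is not recorded, the characteristics table also cannot show whether the arms had similar surgery.

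The recorded items are poor substitutes. Operative length and blood loss are measured after randomization and may be affected by pressure. The text under Visit 3 itself allows that visualization at 12 mmHg may be inadequate. Adjusting for length could therefore remove part of the effect under study.

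**Working it through.** **Inputs from the Statistical Analysis Plan:** means 17 and 29 mm, SDs 20 and 24 mm, 50 per arm, 10% loss. The plan does not say that the means are VAS scores; I take them to be.

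**Assumptions, not in the documents:** two-sided 5% test; two procedure classes; a share p of 30% to 50% in the major class; a pain gap g between classes of 5 to 20 mm; planning SDs that already include the variation between procedures.

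**1. The plan's own figures.** Pooled SD = √((20² + 24²)/2) = √488 = 22.09 mm. Effect size = 12/22.09 = 0.543, which matches the stated 0.54. Ten blocks of ten fill the 100 places. After 10% loss, 50 × 0.9 = 45 per arm. The 50 per group cannot be confirmed, because alpha, sidedness and power are not stated; this point does not depend on it.

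**2. Power without adjustment.** The two-sided 5% t-test at effect size 0.543 has 77% power with 50 per arm and 72% with 45.

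**3. Power with procedure class in the model.** Share of variance due to class: R² = p(1 − p)g²/488. Residual SD = 22.09 × √(1 − R²). Each range below runs from p = 30% to p = 50%.

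| Gap g | R² | Residual SD (mm) | Power, 45 per arm |
|---|---|---|---|
| Unadjusted | – | 22.09 | 72% |
| 5 mm | 1.1-1.3% | 21.97-21.95 | 73% |
| 10 mm | 4.3-5.1% | 21.61-21.52 | 74% |
| 15 mm | 9.7-11.5% | 20.99-20.78 | 76-77% |
| 20 mm | 17.2-20.5% | 20.10-19.70 | 80-82% |

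Example, p = 50% and g = 20: R² = 0.25 × 400/488 = 0.205; residual SD = 22.09 × √0.795 = 19.70; effect size = 12/19.70 = 0.609; power 82%. Going from 88 to 87 degrees of freedom changes power by less than 0.1 point.

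**4. Chance imbalance in the mix.** This is hypergeometric, with 100 patients and 50 per arm.
- The expected absolute difference in the major share is 7.2 points (p = 30%) to 7.9 points (p = 50%).
- With gaps of 15 to 20 mm, that is 0.072 × 15 = 1.1 mm to 0.079 × 20 = 1.6 mm.
- A difference of 20 points or more has probability 5% to 7%. With a 20 mm gap, 20 points is 0.20 × 20 = 4.0 mm.
- The standard error of the mean difference at 50 per arm is 22.09 × √(2/50) = 4.4 mm. It already contains these chance differences.

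**The case against.** **The population may be narrower than it looks.** The insufflation sentence can be read as saying that insufflation is routine in such surgery, not as an eligibility rule. Text not available here may restrict the procedure. This stands as a condition: with a single eligible procedure there is nothing to adjust for.

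**The operation may be recorded anyway.** The Visit 2 list is headed as procedure details and introduced with open wording. Indication is known before surgery and is a partial proxy. This also stands. It answers the recording part, but the planned analysis still has no procedure term.

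**Chance imbalance is not an error.** A reader might infer that an unbalanced mix biases the comparison or shifts the result by 2 to 4 mm. The documents do not support that. Blocked randomization with an unadjusted t-test keeps its type I error, and the standard error already covers chance differences in mix. The 2 to 4 mm figure also needs an imbalance of 12 to 20 points and an assumed gap of 15 to 20 mm, which is larger than the planned 12 mm effect. The expected shift under those gaps is 1.1 to 1.6 mm.

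**Stratified allocation may be moot.** A reader might also infer that separate allocation lists are required. The plan describes randomization in the past tense, and the ten blocks fill the trial, so there may be no allocations left. In a trial of 100, stratification is in any case a matter of preference. This objection stands, and what remains is the covariate.

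**Conclusion.** The point holds as a low-cost gain in precision. As shown, procedure type has no place in the allocation or the model and is not explicitly listed for recording. The absence of strata is read from silence, supported by a block count that fills one list of 100.

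The gain ranges from negligible to useful. Power rises by one to two points with a 5-10 mm gap between procedure classes, and by roughly four to ten points with a 15-20 mm gap. These figures rest on the assumed mix, gap and two-sided 5% test, and on the planning SDs already reflecting mixed procedures, which the documents do not state. The planned t-test is not invalid, and its estimate is not biased by the unstratified allocation.

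**What to change.** 1. Record the procedure class planned before surgery, for example hysterectomy versus other. Allocation takes place after anesthesia, so this can be entered beforehand. For patients already randomized, take the planned class from the pre-surgery chart, not from the operation as performed.
2. Show planned class by arm in the table of characteristics.
3. Replace the unadjusted t-test for VAS with a linear model containing arm and planned procedure class. Fix the classes and the model before outcome data are compared by arm.
4. State that operative length and blood loss will not be used as adjustment covariates.

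The cost is one field (a chart look-up for earlier patients) and one degree of freedom. Stratifying any remaining allocations by class is optional; it would need a second list and might leave the final split slightly unequal. If eligibility is limited to a single procedure, say so in the plan; no change is then needed.

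### Does testing baseline characteristics, while leaving the sized pain score unnamed, call for a change to the SAP?

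*Combined protocol and SAP*

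**What the plan says.** The Statistical Analysis Plan has two short paragraphs. The first sizes the trial at 50 per group from means of 17 mm (SD 20) and 29 mm (SD 24), an effect size of 0.54, "accounting for expected loss to follow up of 10" per cent. It does not say what is measured in millimetres, when it is measured, or at what alpha, sidedness or power.

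The second paragraph begins "We will provide a table of demographic and clinical characteristics by assigned group". Two sentences on method follow: "For continuous variables, we will provide means and standard deviations per group, applying a t-test for comparison of independent means" and "For categorical variables, we will provide counts and percentages, applying chi-square test for comparison of proportions". Neither names a variable, and no other analysis is described.

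The baseline items are listed under Visit 1 (Day 0), starting with "age, race, ethnicity, insurance status (public vs. private), body mass index (BMI), additional medical health conditions" and continuing through surgical, pain, opioid, alcohol, tobacco and mood history. Allocation comes afterwards, under Visit 2 (Day 1): "Post-anesthesia randomization to group A or group B". The VAS appears once, in the post-operative assessment list of that same visit: "surgical complications, estimated blood loss, pathology, visual analog scale (VAS". Visit 3 does not list it.

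**The concern.** On the face of it the SAP tests the wrong things. Visit 1 items are fixed before allocation, so the assigned pressure cannot have affected them. If randomisation was carried out properly, any difference between the arms is chance, and a p-value on it answers no question of the trial. With a dozen or more items, a chance significant result is quite likely. It could be misread as failed randomisation or prompt an unplanned adjustment. Non-significant results could equally be misread as proof of balance.

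Meanwhile, no sentence ties a test to the comparison the trial was sized for. If the two tests cover only the characteristics table, the pain comparison has no stated analysis. If they cover everything, it is one unlabelled row among many. An outcome, time point and sidedness left open could be settled after the data are seen. An allowance for loss to follow-up also sits a little oddly with a score listed only on Day 1.

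**Working it through.** **The plan's own figure.** Inputs from the Statistical Analysis Plan: means 17 and 29 mm, SDs 20 and 24 mm.

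- Pooled SD = √((20² + 24²)/2) = √488 = 22.09 mm.
- Effect size = (29 − 17)/22.09 = 0.543, which agrees with the stated 0.54.

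The planned comparison is therefore one of two independent means, which is what the SAP's t-test does.

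**Are baseline items tested under every reading?** If the two method sentences refer only to the table, yes. If they also cover outcomes, still yes, because the table is included. The observation does not depend on how the paragraph is read.

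**How often would a chance finding appear?** Visit 1 gives 12 items if alcohol/tobacco and depression/anxiety are each counted once, and 14 if both are split. The SAP states no alpha, so 5% is assumed. For k independent items the chance of at least one p < 0.05 is 1 − 0.95^k:

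| Items | Chance of at least one |
|---|---|
| 12 | 46% |
| 13 | 49% |
| 14 | 51% |

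A simulation with the SAP's own tests (50 per arm, 2 continuous and 10 yes/no items, no true difference, assumed prevalences 5% to 50%, 20,000 trials per setting) gives:

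| Correlation between items | Chi-square uncorrected | Continuity-corrected |
|---|---|---|
| 0 | 47–48% | 30–33% |
| 0.3 | 44–45% | 28–32% |

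The SAP does not say which chi-square it means, so the supportable range is about 28% to 51%.

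**Does this reach the pain result?** The smallest imbalance in a continuous item that is significant at 50 per arm is t(98, 0.975) × √(2/50) = 0.397 SD. Suppose an item that far out of balance correlates 0.3 to 0.5 with the VAS (assumed). The VAS difference then moves by:

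- 0.397 × 0.3 × 22.09 = 2.6 mm, to 0.397 × 0.5 × 22.09 = 4.4 mm
- that is 22% to 37% of the planned 12 mm.

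This is a boundary case. Under randomisation, an imbalance that large occurs about 5% of the time per item. The median absolute imbalance is about 0.6745 × √(2/50) = 0.135 SD, which gives:

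- 0.135 × 0.3 × 22.09 = 0.9 mm, to 0.135 × 0.5 × 22.09 = 1.5 mm
- that is 7% to 12% of 12 mm.

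The standard error of the VAS difference with 50 per arm is 22.09 × √(2/50) = 4.4 mm. Even the boundary shift is no larger than one standard error. That standard error already contains the chance imbalance in prognostic factors, so the shift is not bias. Leaving out the baseline p-values would not reduce it.

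**Can the missing detail be filled?** The sizing figures are in millimetres. The only score in the visible text that would be read in millimetres is the VAS, listed at one visit. The SAP names one test for continuous variables, and it suits that score. The step from millimetres to VAS is an inference, but the visible text offers no competing candidate. The 10% allowance may be ordinary padding for missing data, which would fit a Day 1 reading.

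**The case for a change.** The strongest case for acting is that the remedy costs almost nothing: a sentence describing baseline without tests, and another naming the VAS at one post-operative time as primary, with a mean difference, 95% confidence interval, alpha and sidedness. Leaving these open allows choices after the data are seen. Sidedness has consequences: with 45 evaluable per arm, power for the sized difference is about 72% at two-sided 5% and 82% at one-sided 5%.

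Much of this stands. The baseline tests are superfluous, and the visible SAP is thinner than one would like. Three things limit its force.

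- The SAP does not use baseline p-values to choose covariates, to claim balance or to alter any conclusion, so the harm lies in a possible misreading and not in the analysis.
- The power figures concern the sample size, a separate question. The SAP states no power target, so none is shown to be missed, and dropping baseline tests would not change them.
- Part of the document ahead of the Study Protocol section is not in the text available for review. An outcome may be named there, so the gap is established only for what can be read.

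**Conclusion.** The description is accurate, but no change to the plan is needed. Baseline p-values are a redundant reporting habit. At an assumed 5% level they give about a 28% to 51% chance of at least one spurious flag, and nothing planned depends on them. The pain estimate, its standard error and its error rate are the same with or without them. The possible 2.6 to 4.4 mm shift is a boundary case, rests on assumed correlations, and is already allowed for in the t-test.

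The unnamed score, hour, alpha and sidedness are missing detail. A sensible analyst would apply the SAP's t-test to the post-operative VAS by assigned group. This conclusion rests on three assumptions: that the millimetre figures refer to the VAS, that the method sentences extend to outcomes, and that baseline results are read as description.

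### The only test named for continuous data is an unadjusted t-test; a prespecified ANCOVA on BMI, chronic pain and opioid history could sharpen the VAS comparison with no new data

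*Combined protocol and SAP*

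**What the plan says.** The second paragraph of the Statistical Analysis Plan promises a table of characteristics by group and then gives the method: "For continuous variables, we will provide means and standard deviations per group, applying a t-test for comparison of independent means". Categorical variables get a chi-square test. No covariate, regression model or stratified analysis is mentioned anywhere.

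Visit 1 (Day 0) collects BMI, pre-operative opioid or analgesic medication, and "history of chronic pain, history of prior chronic opioid use". Randomisation comes later, at Visit 2 (Day 1): "Post-anesthesia randomization to group A or group B". The Study Protocol section says that "the randomization of the subjects to 12 mmHg (group B) or 15 mmHg (group A) will not be dependent on their BMI". The first paragraph of the SAP describes the allocation: "Patients were randomized using 10 block groups of size 10 each". Ten blocks of 10 exactly fill the 100 planned places, and no strata are mentioned.

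**The concern.** The plan records several plausible predictors of post-operative pain before randomisation, and uses none of them in either the allocation or the named analysis. Whatever VAS variance they explain stays in the error term, which widens the confidence interval and lowers power. Blocking balances arm sizes, not patient characteristics. The t-test's standard error allows for chance imbalance on average, but the estimate from the realised sample is not corrected for it.

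This matters more because the trial may have little power to spare. Alpha, sidedness and target power are not stated. If the test is two-sided at 5%, the planned size falls short of 80% power once the expected losses occur.

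**Working it through.** **Inputs from the SAP, first paragraph.** Means 17 mm (SD 20) and 29 mm (SD 24); 50 per group; 10% loss to follow-up, so n = 50 × 0.90 = 45 evaluable per group.

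**Assumed, because the documents do not say.** Alpha 5%, both one- and two-sided; three covariates (p = 3); R², the share of within-arm VAS variance they explain, from 0 to 0.25.

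**The plan's own effect size.** SD = √((20² + 24²)/2) = 22.09 mm, so d = 12/22.09 = 0.543. This agrees with the SAP, which plans "with an anticipated effect size of 0.54".

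**Unadjusted t-test.** SE = 22.09 × √(2/45) = 4.66 mm on 88 df. The expected 95% CI half-width is 1.987 × 4.66 = 9.26 mm. Noncentral-t power is 72.2% two-sided and 81.9% one-sided.

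**ANCOVA.** The residual variance is multiplied by (1 − R²). The cost of estimating covariate effects multiplies the variance of the treatment difference by 1 + p/(2n − p − 3) = 1 + 3/84 = 1.036, and df fall to 2n − 2 − p = 85. For example, at R² 0.20, SE = 4.66 × √(0.80 × 1.036) = 4.24 mm, and the half-width is 1.988 × 4.24 = 8.43 mm.

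| Analysis | 95% CI half-width (mm) | Power, two-sided 5% | Power, one-sided 5% | Unadjusted n per group with the same two-sided power |
|---|---|---|---|---|
| t-test | 9.26 | 72.2% | 81.9% | 45 |
| ANCOVA, R² 0 | 9.42 | 70.7% | 80.7% | below 45 |
| ANCOVA, R² 0.05 | 9.18 | 72.8% | 82.4% | 45.7 |
| ANCOVA, R² 0.10 | 8.94 | 75.1% | 84.2% | 48.2 |
| ANCOVA, R² 0.20 | 8.43 | 79.9% | 87.8% | 54.1 |
| ANCOVA, R² 0.25 | 8.16 | 82.4% | 89.5% | 57.6 |

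The R² at which ANCOVA power equals t-test power is 0.035, one- or two-sided.

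**Simulation check.** In 20,000 runs with SDs 20 and 24, one continuous covariate and two binary ones (assumed prevalences 20% and 15%), ANCOVA power was 70.7%, 72.7%, 75.3%, 79.3% and 82.0% at the same R² values. Type I error was 4.9% for ANCOVA and 5.0% for the t-test.

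**Chance imbalance.** Taking the number with chronic pain in each arm as binomial with n = 45, the arms differ by 5 or more patients with probability 11%, 23% or 30% at assumed prevalences of 10%, 20% or 30%.

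**The case against.** The strongest reply is that nothing here is an error. The t-test is valid, and no passage links BMI, chronic pain or opioid history to VAS. At R² 0.05 the gain is about 0.7 points of power and 0.07 mm of half-width. Gains of 8 to 10 points need R² of 0.20 to 0.25, which the documents do not support. This stands as a limit on size: the benefit may be negligible. It does not remove the asymmetry between a small, bounded loss and a possibly useful gain.

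Second, the t-test sentence directly follows the one on the characteristics table and names no outcome, so it may describe only that table. That is a fair reading. Applying it to VAS is an inference from the absence of any other method and from a sample size based on a mean difference in mm. On the narrower reading no method is given for VAS at all, and an adjusted analysis is still absent.

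Third, an ANCOVA needs practical rules. Covariates are copied from medical records and some may be missing. If a complete-case analysis lost one patient per arm (44 per group), power at R² 0.05 would be 71.8%, just below the unadjusted 72.2%. At R² 0.10 the gain survives the loss of two per arm (43 per group, 73.1%). VAS is listed without a time point, and the pre-operative medication item mixes opioids with other analgesics. These points shape the wording of the fix but do not defeat it.

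Finally, the imbalance probabilities rest on assumed prevalences and are not converted into mm of VAS, so they are only illustrative.

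**Conclusion.** The concern holds as an efficiency point. The only test named for continuous data ignores covariates that the trial already records before randomisation, and the design does not use them either. At 45 evaluable per group and a two-sided 5% test, adjusting for three covariates changes power by −1.5 points at R² 0, +2.9 at 0.10, +7.7 at 0.20 and +10.2 at 0.25. At R² 0.20 that is worth about 9 more evaluable patients per arm (54 − 45). These figures rest on the SAP's means, SDs and loss rate, and on assumed alpha, sidedness and R². That VAS is the outcome concerned is inferred from the mm scale. The change is worth making, but the documents do not show that the gain will be large.

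**What to change.** Add one paragraph to the SAP that:

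- makes the main VAS comparison a linear model (ANCOVA) of VAS, at a named time point, on assigned group, BMI (continuous), history of chronic pain (yes/no) and prior chronic or pre-operative opioid use (yes/no);
- reports the adjusted mean difference with its 95% CI, and keeps the unadjusted t-test as a sensitivity analysis;
- gives a coding rule for the opioid variable, and a rule for missing covariates that keeps every patient with a VAS value in the model, such as filling in a simple value without reference to outcome or arm;
- states, with a date, that the covariate list was fixed without sight of outcomes by arm.

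The last item matters because the SAP describes randomisation in the past tense, so data may already exist. If outcomes have been seen by arm, the adjusted analysis can no longer be called prespecified.

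All variables are already collected, so the cost is the drafting. If no covariate predicts pain, the loss is about 1.5 points of two-sided power (1.2 one-sided), or about 0.2 mm of half-width.
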